11.0 Specimen Collection and Banking (if applicable)

Sources of Research Material:

1. The material used for analysis in this protocol is of a verbal report, biologic specimen, and brain images. All reports will be collected directly from the patients during the course of their participation in this study. Verbal report data will be collected from direct subject interview, questionnaires, and computer tasks. Biologic samples include urine samples. Urine samples are provided by natural means. Urine samples will be tested for metabolites in the CDAP laboratory located on the first floor of the Institute of Psychiatry.
2. Upon their enrollment in the study, subjects will be assigned a study identification number that will subsequently be used to identify their data in lieu of other personal identifiers. Only the study PI(s) will have access to the database linking subjects’ names to their identification numbers.
3. Data generated during the course of this study will be used for research purposes only. All data will be collected and transferred according to HIPAA guidelines.

12.0 Data Management

Data management, acquisition, and transmission:

The Principal Investigator (PI) will be the primary party responsible for management, oversight, and accountability in terms of participant safety and consent. A conflict of interest will be avoided by secondary evaluation of records by a Monitoring Entity (ME) (aka. data safety monitoring board- DSMB) on a semi-annual basis. This Entity’s reporting will be supported by the South Carolina Translational Research Institute, MUSC’s CTSA. Quality control will include regular data verification (Integrity of the Consent and HIPAA, scores on the Assessments, MRI scanning information), study progress and subject status, any adverse events, and any protocol deviations. Protocol adherence will be monitored by the MUSC Institutional Review Board, who will also be given access to the reports from the PI to the ME.

Data entry methods:

Data will be collected using REDCap™, and entered directly into the online portal to ensure security and prevent data loss.

13.0 Provisions to Monitor the Data to Ensure the Safety of Subjects (if applicable)

Quality control will include regular data verification (Integrity of the Consent and HIPPA, scores on the Assessments), study progress and subject status, any adverse events, and any protocol deviations. Protocol adherence will be monitored by the MUSC Institutional Review Board, who will also be given access to the reports from the PI.

Responsible Conduct in Research Resources: At MUSC all faculty members and staff engaged in research must take an annual Responsible Conduct in research training module which includes the Collaborative Institutional Training Initiative on Protection of Human Subjects (<https://www.citiprogram.org/>) as well as modules customized to the facilities and expectations at MUSC. These resources, coupled with cross-departmental seminar series and NIH funded training opportunities in ethical conduct in research, provide an environment at the Medical University of South Carolina for [name] and the other study personnel on this proposal to obtain required annual training in human research ethics.

All key personnel will undergo appropriate IRB training for dealing with human participants and will be trained by the PI in all aspects of the study interventions. Personnel listed in this protocol (as well as any rotating medical students, graduate students, psychiatry residents or fellows that may be exposed to this investigation as part of their research training exposre) will be required to maintain their certification of HIPPA training and Protection of Human Participants in Research training on an annual basis. Any new personnel without experience in human clinical research will be encouraged to attend the MUSC Core Clinical Research Training Course, which is offered live and online throughout the year. Through these measures we will ensure that all study staff will be trained and will maintain ongoing understanding of research ethics and the rights of the participant during the consenting process and throughout an individual's participation in the study.

Data analysis plan:

Data for this study (behavioral assessments, functional MRI measurements) will be acquired by the members of the [name] lab, including graduate students and research specialists. These individuals will also perform data under the guidance of the PI. Manuscript composition will be led by the PI, with the assistance of the research team.

Quality assurance plan:

The PI has weekly meetings with the research team to discuss qualitative comments received during data collection and any problems in data collection. Initial data analyses will examine distributions of variable scores, and comparability of baseline characteristics across conditions in case analyses need to be adjusted for these. Confidentiality protections are outlined below.

Statistical review of the study, will be conducted by a faculty member from the MUSC Provost-sponsored Biostatistical Collaborative Unit (see Facilities) (including enrollment, retention, assessment inventories) annually. Data collected in previous studies by our research group have demonstrated that after extended use in the MRI scanner environment (likely more than 5000 pulses) the strength of the induced magnetic field from the Magstim biphasic coil begins to drop in a non-linear fashion. Consequently, the intensity of the induced magnetic field from the Magstim coil will be assessed by study personnel and logged weekly (alongside with use records from that week, number of pulses, intensity of pulses). This cumulative record of coil performance will be monitored and, when the intensity of the induced field had degraded 10%, we will switch to a new, identical Magstim coil. We do not anticipate this will occur within the 2-year period of this project.

Confidentiality and Privacy:

Section 301(d) of the Public Health Service Act, November 4, 1988 provides a layer of protection for health data reported by participants that have volunteered for federally funded research studies. Only members of the research team will have access to participant records. Records will be kept in a locked file cabinet in a locked office. Computer records are password protected and will identify participants by Patient ID number.

Definition and Reporting of AEs/SAEs to the IRB/FDA/NIDA:

An AE is defined as any untoward medical occurrence in a study subject administered rTMS that does not necessarily have a causal relationship with this treatment. Any unwanted change, physically, psychologically or behaviorally, that occurs in a study participant during the course of the trial is an adverse event. A Serious Adverse Event (SAE) is defined as an adverse event that has one of the following outcomes: death, life-threatening, inpatient hospitalization or prolongation of existing hospitalization, persistent or significant disability/incapacity, a congenital anomaly/birth defect.

All unexpected Adverse Events (AEs) will be reported to the MUSC IRB and Committee on Human Research within 48-business hours. Serious AEs will be reported within 24-business hours. Follow-up of all unexpected and serious AEs will also be reported to these agencies. AEs/SAEs are documented and reported as per IRB requirements. Research staff will identify adverse events and obtain all available information to assess severity, seriousness, study relatedness, expectedness, outcome and the need for change or discontinuation in the study intervention. Adverse events are generally documented on AE Logs and AE Case Report Forms (CRFs). Additional relevant AE information if available will be documented in a progress note in the research record as appropriate to allow monitoring and evaluating of the AE. If the AE meets the definition for serious, appropriate SAE protocol specific reporting forms are completed and disseminated to the appropriate persons and within the designated timeframes as indicated above. For each AE/SAE recorded, the research staff will follow the AE/SAE until resolution, stabilization or until the participant is no longer in the study as stated in the protocol. We will report adverse events to the Medical MUSC IRB online per the IRB's guidelines.

Incidental Findings Standard Operating Procedure:

Should an incidental finding occur, the posted CBI policy for incidental findings will be followed first and foremost (as posted on website on February 20, 2019) which states that CBI will:

1. Immediately notify the Principal Investigator (PI) of the study.
2. Request that the MRI technologist on duty transfer the study images to the clinical PACS system and notify the designated CBI radiologist.

Following review, the radiologist will contact the PI, discuss the clinical significance of the findings, and decide whether follow-up contact with the subject is necessary.

Should the radiologist contact the PI in writing and recommend follow-up contact, the PI will do the following:

1. Work with the research staff to identify the participant's name and get contact information
2. Contact one of the Study Personnel with a medical degree (MD or DO) regarding their availability to discuss the findings from the radiologist with the PI and with the participant.
 - a. In the event that the PI and the study physician feel it is most appropriate for the physician to speak with the participant directly, the physician will be provided with the participant information as well as the radiologist report so they can speak with the subject and determine the appropriate course of action

- b. In the event that the PI and the study physician feel comfortable having the PI speak to the participant directly, the PI will contact the participant as soon as possible.
3. A log will be kept for all attempts made to contact the subject along with detailed notes for these attempts

In the event that an obvious neurological abnormality is observed that would comprise the validity of the data for the study, the subject will be excluded upon PI discretion.

Reporting of IRB actions and ME/DSMB reports to NIDA

Any adverse events will be immediately reported to both the MUSC IRB and NIDA should this study (R21 proposal) be awarded. All ME/DSMB reports will be submitted to NIH/NIDA annually.

Report of changes or amendments to the protocol.

Any changes to the proposal/protocol must be approved by NIDA. Any amendments to the IRB protocol associated with the proposed work will be reported to NIDA should this proposal be awarded funding.

Trial stopping rules:

The protocol will immediately be paused following notification of a Serious Adverse Event (SAE). Per MUSC IRB policy, the Institutional Review Board and DSMB will be notified within 24 business hours following the SAE notification. SAEs will be reported to NIDA within 72 hours. Should the reported SAE be confirmed as directly related to the protocol, the trial will be terminated. The device manufacturer will be notified within 72 hours. Of note, there have been no clinical trials that have ever been stopped, nor SAE reported in the literature associated with the MagVenture device.

Conflict of interest

Neither the PI, nor members of the research team have any Conflicts of Interest directly related to this protocol. The rTMS device used for the propose study are manufactured by MagVenture.

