14.0 Withdrawal of Subjects (if applicable)

Risks of psychiatric assessments:

All psychiatric assessments will be conducted by study personnel who have received formal training in clinical interviewing and have worked with substance dependent patients in the past.

Participants may withdraw from the study at any time or may be withdrawn from the study if the PI feels it is in the best interest of the participant. In the event of a medical emergency, a research participant will be transported to the Emergency Department at Medical University of South Carolina, which is within two blocks of the CAIR and the Brain Stimulation Laboratory in the Institute of Psychiatry. If a psychiatric crisis occurs, the Department of Psychiatry will be contacted to arrange for either an emergency outpatient appointment or an in house psychiatric consult.

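### Leaving the study is enough to end follow-up of an adverse event that is still open, even if it is serious or related to rTMS, and exit can follow from the harm

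*Combined protocol and SAP*

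**What the plan says.** Section 13.0, under *Definition and Reporting of AEs/SAEs to the IRB/FDA/NIDA*, sets one follow-up rule for all events: staff will "follow the AE/SAE until resolution, stabilization or until the participant is no longer in the study as stated in the protocol". The definition of an event is broad: "Any unwanted change, physically, psychologically or behaviorally, that occurs in a study participant during the course of the trial is an adverse event". The outcomes that make an event serious include "persistent or significant disability/incapacity". Staff are also to "obtain all available information to assess severity, seriousness, study relatedness, expectedness, outcome and the need for change or discontinuation in the study intervention". Follow-up of unexpected and serious events is reported to the IRB and the human research committee.

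Three other places deal with leaving the study or ending it:

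- Section 14.0: "Participants may withdraw from the study at any time", and a participant "may be withdrawn from the study if the PI feels it is in the best interest of the participant".
- Section 15.0, on seizure risk: a participant who has a seizure may not go on in the study. A physician from the stimulation laboratory evaluates the participant after recovery.
- Section 13.0, *Trial stopping rules*: an SAE pauses the protocol and triggers notice to the IRB, the DSMB and NIDA. "Should the reported SAE be confirmed as directly related to the protocol, the trial will be terminated".

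**The concern.** Safety follow-up exists to learn how a harm ends and whether the treatment caused it. If exit can close the record, and the harm can bring about the exit, the cases that most need an outcome are among those that may lose it. Lasting disability is one of the plan's own seriousness criteria, and it may not be possible to judge it on the day someone leaves.

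The stake is participant safety, together with the completeness of the safety record passed to the IRB, the DSMB and NIDA. It does not concern alpha, power or the comparison of DLPFC, MPFC and sham.

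**Working it through.** The main check is textual.

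**1. Is exit sufficient on its own?** Yes. Resolution, stabilization and exit are joined by *or*, and the sentence covers each AE and SAE alike. The closing reference to the protocol does not narrow it, because no section under review defines when someone is no longer in the study or sets safety contact after that.

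**2. Can exit follow from the harm?**

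| Route | Link to the harm | What limits it |
|---|---|---|
| Seizure, Section 15.0 | Express: the event itself bars continuation | Physician evaluation after recovery, with no duration or later contact stated |
| Withdrawal by investigator or participant, Section 14.0 | Plausible: a harm is a natural reason, but the section names no adverse event | Emergency transport and psychiatric referral, which are acute care |
| Trial termination, Section 13.0 | Inferred: a confirmed related SAE ends the trial, but the text does not say whether participants then count as out of the study, or who follows the SAE | Pause and notices to oversight bodies |

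**3. Does another provision require follow-up after exit?** None found.

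- The sentence on reporting follow-up says who receives it, not how long it lasts.
- The instruction to obtain all available information may lead to later contact in practice but sets no end point.
- Table 1 in Section 10.0, as extracted, shows the last TMS session in week 8 and clinical assessments through week 15, so 15 − 8 = 7 weeks of observation after stimulation. That covers people who stay.

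**4. How many participants?** This cannot be computed. It needs the number of exits multiplied by the share with an SAE or related AE open at exit.

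- *Exits.* The sample size paragraph in Section 10.0 starts from 58 screened, with 10% lost after screening and up to 20% by Week 4: 58 × 0.90 = 52.2, and 52.2 × 0.20 = 10.4. This is an all-cause planning allowance, not a count of harm-driven exits, and no rate is given for exits after Week 4.
- *Share with an open event.* No figure is given, and any value would be a guess.
- *Listed harms.* Headache is put at about 5%. Taking this as a per-participant rate (an assumption) gives 32 × 0.05 = 1.6 people on active rTMS, or 48 × 0.05 = 2.4 if sham is the same. Section 15.0 calls these headaches temporary. It puts hearing-threshold shifts at under 4 hours and most seizures at under 60 seconds, and says syncope recovers spontaneously. Few of these would still be open at an exit decision. Unlisted or lasting harms remain possible.

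**The case against.** The strongest reply is that the clause only permits closure, contradicts nothing else in the plan, and sits within a system that watches serious events closely. An SAE pauses the protocol and goes to outside bodies, which also receive follow-up reports on serious and unexpected events. The IRB requirements that the plan refers to are not among the documents, and the consent pages were removed before review, so either may cover contact after withdrawal. The listed harms would usually be over before anyone left.

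Most of this stands, and it is why the point is small. It does not remove the point: the written rule lets follow-up of an open serious event stop at exit, and oversight notices do not set a duration.

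A reader might infer more than the documents support:

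- *That the plan makes follow-up stop at exit.* It does not. It allows this.
- *That stopping stimulation ends follow-up.* The text lists discontinuing the intervention as a separate decision, so stopping is not by itself an exit.
- *That investigator withdrawal is the main route.* Section 14.0 mentions no adverse event. The only exit expressly tied to a harm is seizure, and that route is partly covered by the physician evaluation.
- *That a related SAE would go unfollowed once the trial ended.* The stopping rules are silent on this, and silence does not show that it would happen.

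**Conclusion.** The point holds as a cheap improvement in participant safety. Leaving the study is a sufficient end point for following any event, with no exception for serious or related ones, and nothing in the text under review requires follow-up of an event still open at exit.

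The number affected cannot be computed and is probably small. That judgement rests on Section 15.0's description of the listed harms as mostly brief. The conclusion also assumes that the IRB requirements and consent text, which were not available, do not already close the gap.

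A reader might go on to infer that the treatment comparison or the study's power is damaged. The documents give no basis for that, and it is not claimed.

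**What to change.** In the adverse-event subsection of Section 13.0, keep exit as an end point for non-serious AEs judged unrelated to rTMS, and add:

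*All SAEs, and AEs not judged unrelated to rTMS, that are open when the participant leaves the study (including by trial termination) will be followed to resolution or stabilization by phone or available records, subject to the participant's consent.*

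The limit to serious or not-unrelated events is needed because the plan counts any unwanted change as an AE. Staff already assess seriousness and relatedness for each event, so no new assessment is added. Phone contact matters because participants also come from the community, and the institution's own charts may not cover them. The incidental-findings procedure, with its physician contact and log of attempts, is a ready model.

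The cost is a small number of extra contacts, which the documents do not allow to be counted, and a protocol amendment. Section 13.0 requires NIDA approval for any change, so the sentence could go in with the next amendment. The fix will not reach participants who decline contact.

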14.0 Withdrawal of Subjects (if applicable)

Risks of psychiatric assessments:

All psychiatric assessments will be conducted by study personnel who have received formal training in clinical interviewing and have worked with substance dependent patients in the past.

Participants may withdraw from the study at any time or may be withdrawn from the study if the PI feels it is in the best interest of the participant. In the event of a medical emergency, a research participant will be transported to the Emergency Department at Medical University of South Carolina, which is within two blocks of the CAIR and the Brain Stimulation Laboratory in the Institute of Psychiatry. If a psychiatric crisis occurs, the Department of Psychiatry will be contacted to arrange for either an emergency outpatient appointment or an in house psychiatric consult.

15.0 Risks to Subjects

Potential risks/benefits for participants

The risks fall into three categories: risks associates with psychological assessment, risks associated with repetitive TMS and risks associated with MRI scanning.

Risks of psychiatric interviewing (minimal risk):

1. Some participants may get emotionally distraught when disclosing sensitive personal stories. Some participants may feel anxiety about disclosing substance use histories and reporting some aspects of their demographics.

Risks associated with MRI scanning (minimal risk):

1. The major potential risks for MRI are all subsumed under the risks for TMS and primarily include risks to individuals who have metallic implants, pacemakers, or pregnant women. These individuals will be excluded from the study.
2. Participants may feel restless or uncomfortable when lying in the MRI scanner.

Risks associated with repetitive TMS (FDA-designated minimal risk):

Potential Risks of TMS

Repetitive TMS has been considered “non-significant risk” by the FDA (2007) when applied at similar intensities, durations, and frequencies to those being used in this protocol. Additionally motor cortex and dorsolateral prefrontal continuous theta burst stimulation in a manner identical to this protocol has been designated minimal risk by the MUSC Institutional Review Board for healthy adults as well as individuals with opiate dependence.

Potential risk of a seizure:

In designing this experiment, we have followed the latest safety guidelines for TMS. Despite these precautions, there is a chance of a seizure as a result of rTMS. Eight seizures have been noted in previous studies, with six of them occurring in healthy volunteers without any history of seizures, brain tumors or traumatic brain injuries. All of these seizures have occurred during rTMS with the participant in the treatment chair and a trained operator on hand. All seizures have stopped by themselves without any medication. No participants have had any problems after the seizures. MUSC has a plan for dealing with fainting and seizures, and **every TMS researcher involved in providing TMS treatment for this protocol (Key Personnel) will have to attend the MUSC Brain Stimulation Intensive training program wherein they will receive a Certificate of Completion after a written test of TMS didactics and safety measures** as well as a skills test associated with collecting an accurate motor threshold (which is one of the largest factors that promotes safety). Additionally, if a participant has a seizure an emergency response team will be called. Most seizures, including those caused by rTMS, last less than 60 seconds and do not require any medication. Participants will be evaluated by a physician associated with the MUSC Brain Stimulation Laboratory following recovery from the seizure. Any participant who has a seizure cannot continue with the study.

Other potential risks:

1. **Potential for scalp discomfort and headaches:** Some people report mild discomfort when the magnetic pulses are applied over the scalp. A small number of people (~5%) report headache following rTMS. However, the headaches are temporary and manageable with common over-the-counter pain remedies.
2. **Potential hearing loss:** The TMS coil generates a high-energy click that may cause hearing damage. Humans exposed to TMS have shown temporary increases in auditory threshold (especially at high frequencies) lasting at least 5 minutes and less than 4 hours.
3. **Safety in case of pregnancy:** This protocol will exclude pregnant women. The risks of using TMS with pregnant women are currently unknown. Please inform the research team if you are pregnant or think that you might have become pregnant during the study. A pregnancy test will be performed before the experiment begins.

4. Potential for reflex syncopal event: Syncope is defined as a momentary loss of awareness and postural tone. It typically has a rapid onset, short duration, and spontaneous recovery. Although syncopal episodes are very rare with TMS (less than 1%), they typically occur during the motor threshold procedure before the rTMS treatment has begun. Individuals that are sleep deprived and have low or unstable blood pressure are at greater risk.
5. Interaction with electrical or metal implants: Electrically, magnetically or mechanically activated implants (such as cardiac pacemakers), as well as clips on blood vessels in the brain may be affected by rTMS (as well as MRI) and cause pain or abnormal signal propagation. Therefore individuals that have these implants and devices or suspect that they may have pieces of metal in their eyes, head, or body (e.g. bullets, shrapnel, fragments from metallurgy) will be excluded from the study.

